1.0 Introduction

Postoperative urinary retention (POUR) is a common complication following certain surgical operations. While much is known about the innervation and neural regulation of bladder emptying and storage, the cause of urinary retention after surgery is not fully understood. Early research has indicated that a small dose of tamsulosin (Flomax®), a commonly used medication approved to treat urinary symptoms in men with benign prostatic hypertrophy, may reduce the incidence of POUR. Urinary retention is a prevalent issue in patients undergoing spinal surgery, leading to patient discomfort and prolonged length of stay. We hypothesize that the use of perioperative tamsulosin in patients undergoing spinal surgery will decrease the incidence of POUR.

2.0 Background

In the United States, estimates of POUR rates range from 2% to 70%[1, 2]. This wide range is due to multiple factors affecting its incidence, including anesthetic regimen, duration and type of surgery, age, gender, co-morbidities and presence of pre-operative urinary symptoms[2]. There is a paucity of literature specific to spine patients, but published rates in this population range from 5% to 38%[3-5]. POUR can be painful, physically damaging, and emotionally troubling for patients.

Up to 22% of patients that develop POUR receive an intra-urethral catheter[6], which places them at an increased risk of developing hospital-acquired urinary tract infections. These catheter-associated urinary tract infections (CAUTIs) significantly contribute to patient morbidity, increase the average length of hospital stay, and are associated with increased inpatient mortality[2, 7]. CAUTIs also have a significant financial impact, costing U.S. hospitals an estimated \$400 million annually[8]. This is especially significant since the Centers for Medicare and Medicaid no longer compensate hospitals for the additional cost of treating CAUTIs, believing them to be reasonably preventable[9].

The exact pathogenesis of POUR is not well understood. One theory is that over-activation of alpha-adrenergic nerve receptors on the human bladder is an important contributor to urinary retention after surgery[10]. This theory is based on current understanding of bladder physiology and the fact that many agents such as ephedrine used during general anesthesia have activity at alpha-adrenergic receptors. Patients treated with ephedrine have been shown to be at increased risk of developing urinary retention [11, 12].

Tamsulosin, a medication that blocks these alpha-adrenergic receptors, has been shown to significantly reduce the incidence of POUR in specific surgeries when given preoperatively[13-15]. This drug, which is FDA approved and widely used to treat symptoms of bladder outlet obstruction and benign prostatic hypertrophy (BPH) in males, has a favorable side effect profile and a half-life of 9-15 hours, achieving steady state after 5 days with daily dosing[16]. While previous studies have demonstrated the practicality, efficacy, and safety of prophylactic tamsulosin for POUR, the trials were small and only examined urinary retention in patients undergoing hernia repair and other general surgical procedures; no spinal surgery patients were included in these trials.

Madani and colleagues had the largest trial, randomizing 232 male patients undergoing inguinal or scrotal surgery to either tamsulosin or placebo[14]. While they found that tamsulosin dramatically reduced the incidence of POUR (5.9% with tamsulosin vs 21.1% with placebo; $p = .001$), the patient population differs from our spine patients. This study also excluded patients with excessive perioperative fluid intake and duration of surgery greater than 90 minutes, both of which are populations at risk for POUR and therefore should be studied. Mohammadi-Fallah and colleagues found a similar reduction in POUR in their randomized trial (2.5% with tamsulosin vs 15% with placebo; $p = .04$), though the numbers were very small ($n=80$) and the patient population underwent inguinal herniorrhaphy[13]. Both of these studies administered study drug no more than 14 hours prior to surgery. The third and most recent study by Poylin and colleagues was a retrospective review in men undergoing pelvic surgery; tamsulosin was given at the discretion of the surgeon 3 days prior to surgery[15]. Their findings were in line with previous work, with a rate of POUR of 6.7% in the tamsulosin group and 25% in the control group ($p = .029$). In none of these studies were there complications or adverse events attributable to tamsulosin.

At Maine Medical Center (MMC), there are approximately 2600 elective spinal surgeries annually. Nearly half of these patients are males over age 50, who have an increased risk of developing POUR[3]. Over the past three years, over 1900 males aged 50 years or greater have undergone elective spinal surgery at MMC, and within this group approximately 17% have developed POUR.

Currently, the administration of preoperative prophylactic tamsulosin is standard practice at MMP Orthopedics, given to high risk male patients who are undergoing total joint replacement. A modified version of the International Prostate Symptom Score is administered preoperatively, and if the score is ≥ 6 , these patients are given a course of tamsulosin (3 days preop and continuing 7 days after discharge). Although they have no formal data, providers and nursing staff believe the incidence of POUR has decreased substantially, and aside from occasional episodes of transient hypotension, there have been no safety issues with this practice.

We propose a randomized, double-blinded, placebo-controlled investigation of the impact of perioperative tamsulosin on the incidence of POUR in patients undergoing elective spine surgery.

3.0 Study Objectives

3.1 Primary Objective

This trial will test the hypothesis that prophylactic administration of tamsulosin will reduce the incidence of POUR compared to placebo, and will not increase the risk of adverse events in this setting.

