6.2 Outpatient procedures

After patient consent is obtained, all study patients will undergo a non-invasive post-void bladder scan via portable ultrasound to measure PVR. In addition, study staff will obtain a modified International Prostate Symptom Score (IPSS), a short survey to measure baseline lower urinary tract symptoms[17].

At this time, patients will also have orthostatic blood pressure measurements taken as follows:

- BP and pulse taken while patient is laying down and sitting
- BP and pulse taken after patient goes from sitting to standing

If patient meets definition of having orthostatic hypotension as described in 5.2 Exclusion Criteria, he will be excluded from study participation. A record of all patients screened and excluded for this reason will be kept with study documents. After PVR, BP and IPSS, patient will be given prescription for 7 days of study drug. Patient will be instructed to begin once daily evening administration of study drug five days prior to surgery, and to continue self-medication up to and including the night before surgery. Patients will record study drug administration on a drug diary card, given by office staff. Patient will be instructed to keep two doses at home for possible dosing after surgery, depending on discharge date. Patient and office providers will be blinded to the assigned medication.

Computer-generated 1:1 randomization (without blocking) will be done by the MMC pharmacy, which will place a seven day supply of tamsulosin 0.4 mg or placebo in sequentially numbered envelopes corresponding to study ID prior to study start. Study drug will be kept in and dispensed from locked cabinet in research coordinator's office. Study staff will access locked cabinet and pull next available envelope to give to consented patient. Study ID number will be logged into study binder kept in locked cabinet.

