6.6 Follow-up

Patients discharged before full course of study drug is given (two postoperative doses) will be instructed to take study drug at home as outlined on patient instruction card, specifically: Patients discharged on day of surgery will take two doses at home (on day 0 and day 1 postop); patients discharged on day 1 postop will take one dose at home; and patients discharged after day 1 postop will not take any study drug. Patients will be advised to discard remaining study drug.

As part of standard of care, it is routine for nursing staff at MMP NSS to follow up with patients via phone call within 24 hours of discharge. As a part of this call, all study patients will be queried on any issues related to urinary retention. They will also be asked if they have continued their study medication as instructed.

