8.2 Secondary Outcome

Secondary outcome measures to be examined are length of stay, relationship between pre-operative PVR and POUR, correlation of baseline IPSS and POUR, relationship of surgical time to POUR, and time to first spontaneous void.

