10.2 Sample Size and Power Calculations

Tamsulosin is hypothesized to reduce POUR compared to placebo in males. Observational data from our center shows a POUR rate of about 17% in patients similar to those to be included in the trial. We hypothesize that the use of the drug can reduce this rate by 50%. A two group continuity corrected c^2 test with a 0.050 two-sided significance level will have 80% power to detect the difference between a control group proportion of 0.170 and a treatment group proportion of 0.085 (odds ratio of 0.454) when the sample size in each group is 264 and a total sample size of 528.

We anticipate recruiting 264 evaluable patients in each group who took at least one dose of study drug and who also had surgery. Due to expected patient drop-out (from surgery cancellations, patients changing their mind or forgetting to take study drug), we expect to enroll up to 610 patients to achieve this.

In a recent chart review, it was found that 670 potentially eligible male patients (age 50-85 and not on preoperative tamsulosin) were seen at MMP NSS in FY 2014, and 680 were seen in FY 2015. Given this volume of patients undergoing spine surgery at MMC, it seems reasonable to expect we could accrue our target enrollment in three years.

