10.3 Randomization

To evaluate the success of randomization, characteristics of patients in the treatment and control groups will be compared using t-tests or their non-parametric equivalents, as appropriate, for continuous variables and chi-square tests or Fisher's exact tests, as appropriate, for categorical variables. The primary outcome, incidence of POUR, will be compared across groups using chi-square tests. If large baseline imbalances between groups are found, a secondary analysis will be performed using a logistic regression model, with POUR as the outcome variable, treatment group as the predictor of interest, and imbalanced patient characteristics as confounding variables. Secondary objectives examine the relationship between other factors and POUR and will be analyzed similarly. Length of stay and time to first void will be analyzed as continuous variables, using t-tests and linear regression models.

REFERENCES

1. Wu, A.K., A.D. Auerbach, and D.S. Aaronson, *National incidence and outcomes of postoperative urinary retention in the Surgical Care Improvement Project*. Am J Surg, 2012. **204**(2): p. 167-71.
2. Baldini, G., et al., *Postoperative urinary retention: anesthetic and perioperative considerations*. Anesthesiology, 2009. **110**(5): p. 1139-57.
3. Boulis, N.M., et al., *Urinary retention following routine neurosurgical spine procedures*. Surg Neurol, 2001. **55**(1): p. 23-7; discussion 27-8.
4. Jung, H.J., et al., *Postoperative urinary retention following anterior cervical spine surgery for degenerative cervical disc diseases*. Clin Orthop Surg, 2013. **5**(2): p. 134-7.

5. Gandhi, S.D., et al., *Patient and surgical factors associated with postoperative urinary retention after lumbar spine surgery*. Spine (Phila Pa 1976), 2014. **39**(22): p. 1905-9.
6. Burger, D.H., et al., *Prevention of urinary retention after general surgery: a controlled trial of carbachol/diazepam versus alfuzosine*. J Am Coll Surg, 1997. **185**(3): p. 234-6.
7. Hooton, T.M., et al., *Diagnosis, prevention, and treatment of catheter-associated urinary tract infection in adults: 2009 International Clinical Practice Guidelines from the Infectious Diseases Society of America*. Clin Infect Dis, 2010. **50**(5): p. 625-63.
8. Scott, R.D. *The Direct Medical Costs of Healthcare-Associated Infections in U.S. Hospitals and the Benefits of Prevention*. 2009 [cited 2015 November 24, 2015].

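### Section 3.1 says the trial will test that tamsulosin does not increase adverse events, but no outcome or analysis compares adverse events between arms, and the protocol text describes no step that elicits non-serious events from the five preoperative home doses

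*Combined protocol and SAP*

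**What the plan says.** Section 3.1 gives the primary objective as a hypothesis in two halves that the trial is to test: tamsulosin lowers the incidence of POUR, "and will not increase the risk of adverse events in this setting".

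The sections that could put the second half into practice deal with other matters:

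- Section 8.1 defines the primary outcome as POUR alone.
- Section 8.2 begins "Secondary outcome measures to be examined are length of stay, relationship between pre-operative PVR and POUR" and goes on to baseline IPSS, surgical time and time to first void. Section 3.2 covers the same ground.
- Section 10.2 sizes the trial for POUR alone and plans for "264 evaluable patients in each group who took at least one dose of study drug and who also had surgery".
- Section 10.3 states "The primary outcome, incidence of POUR, will be compared across groups using chi-square tests". It then covers adjustment for baseline imbalance, factors related to POUR, length of stay and time to void.

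On collection, section 6.2 has men start the drug five evenings before surgery and "continue self-medication up to and including the night before surgery". The record for that period is described as follows: "Patients will record study drug administration on a drug diary card". At the call after discharge in section 6.6, "all study patients will be queried on any issues related to urinary retention", and "They will also be asked if they have continued their study medication as instructed". Section 9.1 promises that all adverse effects will be documented. Section 9.2 covers serious events at any time on study. Section 10.1 lists adverse events among the postoperative data. It refers to an attached data sheet, and section 9.4 to an attached DSMB plan.

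**The concern.** A claim placed in the primary objective needs an outcome, a population and a comparison fixed in advance. Without them, the adverse-event summary at the end of the trial can be put together in several ways. The likely risk is that a non-significant difference is reported as confirming half of the primary objective. Failing to find a difference is not evidence that there is none, least of all in a trial sized for something else.

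Collection adds to the problem. The first dose and four more are taken at home before surgery. Section 9.1 itself gives orthostatic hypotension after a first dose at 6% to 19%. Section 6.2 measures orthostatic blood pressure only before dosing starts. If nobody asks about non-serious symptoms from those days, the safety comparison may miss the period that matters most for this drug.

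**Working it through.** **1. Is the safety half made testable anywhere?** Sections 3.2, 8.1, 8.2, 10.2 and 10.3 were read for an adverse-event outcome, a population for safety and a between-arm comparison. None of the three appears. The outcomes that 10.3 analyses are POUR, length of stay and time to first void, together with the factors related to POUR.

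**2. What was the trial sized for?** Inputs from section 10.2: 0.170 against 0.085, two-sided 0.05, 80% power, continuity correction.

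- Uncorrected n = [1.960 × √(2 × 0.1275 × 0.8725) + 0.842 × √(0.170 × 0.830 + 0.085 × 0.915)]² / 0.085² = 240.5.
- Corrected n = (240.5/4) × [1 + √(1 + 4/(240.5 × 0.085))]² = 263.5, so 264 per arm.

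The stated 264 reproduces exactly. It supports the POUR half of the objective only.

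**3. How much exposure comes before surgery?** Evenings −5 to −1 give 5 doses, and days 0 and 1 give 2 more, 7 in all. This agrees with the seven-day supply and the two doses kept back in section 6.2. Five of seven doses, including the first, are self-administered before surgery.

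**4. Which described step would bring out a non-serious event from those five doses?**

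- Diary card (6.2): described for drug intake.
- Orthostatic blood pressure (6.2): before the first dose.
- Discharge call (6.6): described for retention and adherence.
- Data collection (10.1): adverse events listed with the postoperative items.
- Sections 9.1 and 9.2: a promise to document, and reporting of serious events, without an eliciting procedure for non-serious ones.

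**5. Illustrative precision.** The documents give no placebo adverse-event rate, so every rate here is an assumption, as is complete capture of events. With n per arm and the same true rate p in both arms, the 95% half-width is 1.96 × √(2p(1 − p)/n).

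- p = 15%, n = 264: 1.96 × √(2 × 0.15 × 0.85/264) = 6.1 points.
- Range: 1.7 points at p = 1% to 8.5 points at p = 50%.

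**6. Why non-significance is not support.** Suppose the true rates were 15% and 20%. The chance of a non-significant uncorrected two-sided 5% chi-square test at 264 per arm is about Φ[(1.96 × √(2 × 0.175 × 0.825) − 0.05 × √264)/√(0.15 × 0.85 + 0.20 × 0.80)] = Φ[(1.053 − 0.812)/0.536] = Φ(0.449) = 67%. Exact binomial enumeration gives 67.4%. For the same 5-point increase the exact figure is 7.9% at 1% against 6%, and 79.0% at 50% against 55%. The answer depends on which adverse event is meant, and the text does not say.

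**The case against.** The strongest reply is that safety in such a trial is normally descriptive, that POUR is plainly the only primary outcome and the only sized comparison, and that the clause in 3.1 is loose wording. That is a fair account of the probable intent, but it is also the reason to reword the clause: as written, it says the trial will test something that no analysis tests. It also follows that the lack of a non-inferiority margin is not itself the defect, because estimation needs none.

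Three other objections limit the point.

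- **Collection.** A reader might infer that adverse events are not collected, or that preoperative ones are ignored. The documents do not support that. Sections 9.1 and 9.2 commit to documentation and serious-event reporting, and 10.1 describes prospective collection in the office, at the bedside and by chart review. Recording after surgery can cover events from before it. The data sheet and DSMB plan may hold the missing items. What stands is that the protocol text describes no eliciting step.
- **Population.** A reader might infer that men who take doses and then have surgery cancelled will be dropped from safety summaries. The phrase in 10.2 is a recruitment target for evaluable men, not a safety population. The allowance of 610 − 528 = 82 men also includes those who change their mind or forget the drug, so the number dosed is unknown. What stands is that no safety population is named.
- **Bias.** A reader might infer that the adverse-event comparison will be biased. The trial is double-blind with the same described procedures in both arms, and nothing in the documents shows a direction or size of bias.

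**Conclusion.** The point holds for the protocol text. The safety half of the hypothesis in 3.1 has no matching outcome in 8.1 or 8.2 and no between-arm analysis in 10.3, so it cannot be tested as planned, and a non-significant result would not establish it. This part does not depend on the attachments for its main force: whatever they contain, 3.1 and 10.3 do not match. The second part, that no described step elicits non-serious events from five of the seven doses, is limited to the protocol text because the data sheet and DSMB plan were not seen.

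The size of any effect on the safety conclusion cannot be calculated from the documents. The 6-point half-width rests on an assumed 15% rate, and the wider range of 1.7 to 8.5 points on assumed rates of 1% to 50%. A reader might take these figures to show that the trial is too small for safety. They do not show that, because the answer changes with the endpoint and the rate assumed. The POUR comparison and its sample size stand as they are. The point is worth fixing because it concerns a stated primary objective and the remedy is cheap.

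**What to change.** 1. Reword section 3.1 so that the trial tests whether tamsulosin reduces POUR compared with placebo and estimates the difference in adverse-event risk between the arms.
2. Add to section 10.3: between-arm risk differences with 95% confidence intervals for any adverse event and for any serious adverse event, in all randomized men who took at least one dose, whether or not surgery took place. State there that a non-significant difference will not be read as evidence of no increase.
3. Add a fixed adverse-event question covering the period since the first dose to the existing discharge call in section 6.6 and to the postoperative data recording in 10.1. If the data sheet already asks this, cite it instead.

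The cost is amendment wording, a few added questions and a more modest safety claim. Two limits should be acknowledged. The call, due within 24 hours of discharge, may come before the last dose in men who go home on the day of surgery. No study contact is described when surgery is cancelled, so those men would need a brief query when the cancellation is recorded. Nothing changes in the POUR analysis or the sample size.

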3.2 Secondary Objectives

Secondary analyses will include

- Treatment difference in length of stay
- Treatment difference in time to first spontaneous void

- Relationship between preoperative post-void residual (PVR) and POUR
- Correlation of baseline IPSS and POUR
- Relationship between duration of surgery and POUR

4.0 Design

The study is a prospective, double-blind, randomized, placebo-controlled trial. Subjects will be randomized 1:1 to receive either oral tamsulosin 0.4 mg or placebo, taken once each evening, beginning 5 days prior to surgery and continuing through the first postoperative day. The primary endpoint is met when the patient is able to spontaneously empty their bladder post-operatively, or needs to be catheterized with either a straight or indwelling urinary catheter for post-operative urinary retention, whichever occurs first.

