6.5 Postoperative considerations

Post-operative care of study patients will include orders for the MMC Acute Retention Protocol, as follows:

- If patient has not voided after 4 to 6 hours or is uncomfortable, a bladder scan is done.
- Straight catheterization is done if bladder scan volumes are greater than 300 to 500 cc (defer if patient is known to chronically retain high volumes and is not uncomfortable).

All patients with POUR will be treated as deemed necessary by the medical team. Treatment of any patient that has POUR will not be guided or constrained by this study.

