8.0 Outcome

8.1 Primary Outcome

The primary outcome measure will be post-operative urinary retention, defined as the need for post-operative urinary catheterization for acute retention as defined by the MMC Acute Retention Protocol, or re-catheterization in those patients who leave the operating room with an indwelling catheter.

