10.0 Analytic Methods

10.1 Data collection

Data will be collected prospectively by study staff in the office, at the bedside and through Epic chart review. A study ID will be assigned to each patient and study documents will all use this ID to collect data. Identifiable data will be stored separately. Baseline variables to be collected will include basic demographics, past medical history and medication list, PVR and IPSS. Operative data will include type and duration of surgery, fluid intake, medications given, and any perioperative urinary catheterization. Data will be recorded postoperatively will include fluid balance, need for urinary catheterization, pain medication and adverse events.

All data will be recorded on a data collection sheet (see attached data sheet). PVR and IPSS done in the MMP NSS office will also be recorded on separate forms (see attached PVR and IPSS forms), which will be linked to the primary data collection sheet. These data sheets will be stored in a locked and secure area of the study coordinator's office.

RedCap, a HIPAA-compliant database, will be used to store all information after it is collected. Data entry and access will only be allowed to research coordinator and Principal Investigator.

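### Sections 4.0 and 8.1 give different rules for the primary endpoint: under 4.0 a spontaneous void can settle it, while 8.1 counts catheterisation for retention whether or not a void came first.

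*Combined protocol and SAP*

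**What the plan says.** Section 4.0 (Design) describes the primary endpoint as one of two events: "The primary endpoint is met when the patient is able to spontaneously empty their bladder post-operatively, or needs to be catheterized". The sentence goes on: "or needs to be catheterized with either a straight or indwelling urinary catheter for post-operative urinary retention, whichever occurs first".

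Section 8.1 (Primary Outcome) names one kind of event. POUR is "defined as the need for post-operative urinary catheterization for acute retention as defined by the MMC Acute Retention Protocol, or re-catheterization" in men who leave the operating room with a catheter in place. It does not mention an earlier void.

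Section 6.5 sets out the retention protocol that 8.1 relies on: "If patient has not voided after 4 to 6 hours or is uncomfortable, a bladder scan is done".

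Other sections bear on which reading was intended:

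- Section 3.1 tests whether "prophylactic administration of tamsulosin will reduce the incidence of POUR compared to placebo".
- Section 10.2 is powered on POUR proportions of 0.170 and 0.085, and Section 10.3 compares POUR incidence by chi-square test.
- Sections 3.2 and 8.2 make first void a secondary measure; 8.2 lists "relationship of surgical time to POUR, and time to first spontaneous void".
- Section 10.1 includes "need for urinary catheterization, pain medication and adverse events" among the postoperative data, with no stop at first void.
- Section 6.6 says that at the post-discharge call "all study patients will be queried on any issues related to urinary retention".

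**The concern.** Read literally, Section 4.0 makes a successful void a way of meeting the primary endpoint, so men with and without retention both meet it. The kinder reading is that 4.0 says when a man's status becomes known: a void means no POUR, a catheter for retention means POUR. That removes the oddity but not the conflict. Under a first-event rule, the man who empties his bladder and later needs a catheter for retention has already been settled as free of POUR. Under 8.1 he is a case.

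This is the primary outcome of a double-blind trial. Section 4.0 is the only place that states an ordering rule, and 8.1 is silent on order. Someone classifying a void-then-catheter case would find an explicit rule only in 4.0, and it gives the wrong answer. The main risk is misclassification rather than lost data, because catheterisation is to be recorded regardless.

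**Working it through.** **1. The two rules side by side**

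| Postoperative course | Section 4.0, read as a first-event rule | Section 8.1 |
|---|---|---|
| Empties bladder, never catheterised for retention | Settled by the void: no POUR | No POUR |
| Catheterised for retention before any emptying | POUR | POUR |
| Empties bladder, later catheterised for retention | Settled by the void: no POUR | POUR |

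Only the third row differs.

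**2. Can the third row occur?** Yes. Section 6.5 has two routes to a scan, joined by 'or': no void after 4 to 6 hours, or discomfort. The second does not require that the patient has not voided, so the retention protocol supplies no hidden exception to 8.1. The row is limited to men who have emptied. Section 4.0 gives no criterion for emptying, so a man who passed only a small volume may not be settled by it.

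**3. Reproducing the plan's sample size.** Inputs from Section 10.2: p1 = 0.170, p2 = 0.085, two-sided alpha 0.05, power 80%, continuity-corrected chi-square. The difference is d = 0.085 and the mean proportion is 0.1275.

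- Uncorrected: n0 = [1.960 × √(2 × 0.1275 × 0.8725) + 0.842 × √(0.170 × 0.830 + 0.085 × 0.915)]² / d² = (0.9245 + 0.3937)² / 0.085² = 240.5.
- Corrected: n = (n0/4) × [1 + √(1 + 4/(n0 × d))]² = 263.5, rounded up to 264 per arm.

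The stated 264 per arm is reproduced. It treats POUR as the only event, which fits 8.1 and not the literal wording of 4.0.

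**4. Illustrative size.** The documents do not give the share s of POUR cases catheterised after an earlier emptying. Assume that 4.0 is applied, that the 17% reflects the 8.1 definition, and that the same share is lost in both arms. The rates become 0.170 × (1 − s) and 0.085 × (1 − s), with the relative effect unchanged. Expected cases under 8.1 are 264 × (0.170 + 0.085) = 67.3. Power is by exact enumeration of two binomials with 264 per arm and a two-sided chi-square test at 0.05.

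| Assumed s | Rates | Cases changing status (67.3 × s) | Power, corrected | Power, uncorrected |
|---|---|---|---|---|
| 0% | 0.170 / 0.085 | 0 | 0.808 | 0.844 |
| 5% | 0.1615 / 0.0808 | 3.4 | 0.784 | 0.822 |
| 10% | 0.153 / 0.0765 | 6.7 | 0.757 | 0.797 |
| 20% | 0.136 / 0.068 | 13.5 | 0.695 | 0.741 |

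Power falls below 80% once s passes 1.8% with the correction, or 9.4% without. Section 10.2 plans with the correction; Section 10.3 does not mention one.

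**The case against.** The strongest reply is that 4.0 is a one-sentence design summary, while 8.1 carries the heading for the primary outcome and is worded as a definition. The objective, sample size, test and list of secondary outcomes all agree with 8.1. No analysis could treat both outcomes as events, since nearly every patient would be one. On this view 8.1 already settles the matter and 4.0 is merely loose. This stands as evidence of intent, and 8.1 is probably the intended definition. It does not make the two rules agree, and no text gives 8.1 precedence.

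Second, the group in dispute is narrow. A man who passes a little urine and still scans high has arguably not emptied and would be a case under both sections. That stands, and the size of the remaining group is unknown.

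Third, the power figures rest on assumptions the documents cannot support. The plan does not say how the 17% was ascertained; if it already left out retention after a void, the modelled loss disappears. The 1.8% threshold is low mainly because exact corrected power starts at only 80.8%. Both points stand, so the figures are illustrative and the finding does not depend on them.

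Fourth, removing the first-event wording leaves no end to endpoint observation. Section 10.1 gives no duration, and Section 6.6 offers one call within 24 hours of discharge. This is fair, but 8.1 already lacks a time window as it stands; the change does not create that gap.

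**Conclusion.** The concern holds. The plan has two rules for its primary endpoint, they disagree for men who empty the bladder and are later catheterised for retention, and nothing reconciles them. Following 4.0 as written would misclassify those men. Section 8.1 is probably the intended rule.

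The effect ranges from nothing, if no cases follow an earlier emptying, to about 13 of 67 expected cases and a fall in corrected power from 81% to 70% at an assumed share of 20%. That range requires that 4.0 is actually applied, that the 17% reflects 8.1, and that the loss is proportionally equal in both arms. If 8.1 governs, 264 per arm and 528 in total are unaffected. This should be fixed because it concerns the primary outcome and the repair is cheap, not because a power loss has been shown.

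**What to change.** 1. Replace the endpoint sentence in Section 4.0 with a pointer, for example: *The primary endpoint is POUR as defined in Section 8.1.*
2. Add to Section 8.1 that catheterisation for retention counts as POUR whether or not the patient has already voided. While that section is open, it would be sensible to state the period over which events count, since none is given.
3. Keep first spontaneous void only as the secondary time outcome already listed in Sections 3.2 and 8.2.

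The cost of these changes is protocol wording. They affect how the endpoint is classified and not how patients are managed. Need for catheterisation is already collected under Section 10.1, and the sample size and primary test stay as they are. The wording should be settled before any unblinded data are seen.
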